8.11.4.3 Survival Follow-up Contacts

Survival Follow-up Visits are required for participants that withdraw from treatment for disease progression or have started other anticancer therapy.

Participant Survival Follow-up status will be assessed approximately every 12 weeks to assess for survival status until death, withdrawal of consent, or the end of the study, whichever occurs first.

The first Survival Follow-up assessment should be scheduled as described below:

1. For participants who discontinue treatment intervention and who will not enter Efficacy Follow-up, the first Survival Follow-up contact will be scheduled 12 weeks after the Discontinuation Visit and/or Safety Follow-up Visit (whichever is last).
2. For participants who completed assessments in Efficacy Follow-up, the first Survival Follow-up contact will be scheduled 12 weeks after the last efficacy assessment follow-up visit has been performed.

9 STATISTICAL ANALYSIS PLAN

This section outlines the statistical analysis strategy and procedures for the study. Changes to analyses made after the protocol has been finalized will be documented in a sSAP and referenced in the CSR for the study. Post hoc exploratory analyses will be clearly identified in the CSR.

9.1 Statistical Analysis Plan Summary

Key elements of the SAP are summarized below. The comprehensive plan is provided in Section 9.2 through Section 9.12.

Study Design Overview CCI	A Phase 2, open-label, nonrandomized study to evaluate the safety and efficacy of MK-7684A and vibostolimab monotherapy in participants with various hematological malignancies. The study will be divided into 2 parts: signal finding (Part 1) and cohort expansion (Part 2).
Primary Endpoints	Part 1: Safety assessed by number of participants with and/or rates of: 
• Dose-limiting Toxicities• Adverse Events• Discontinuation of study intervention due to an AE
Secondary Endpoints	Part 1: 
• Objective response rate assessed per disease criteria by investigator• Duration of response as assessed by investigator per relevant disease response criteria (Appendix 8)• Disease control rate as assessed by investigator per relevant disease response criteria (Appendix 8)• Pharmacokinetic endpoints including: C_{trough} and C_{max} Note: CR, PR, and PD in lymphoma participants do not require confirmation. Stringent CR, CR, VGPR, PR, and PD in MM participants require confirmation via 2 consecutive laboratory assessments.
Statistical Methods for Key Efficacy Analyses	Separately for each disease cohort, the point estimate of ORR and DCR will be provided, together with 95% CI using exact binomial method proposed by Clopper and Pearson (1934)[Clopper, C. J. and Pearson, E. S. 1934]. Time to event analyses (DOR) will be based on Kaplan-Meier estimation and corresponding 95% CIs.

Statistical Methods for Key Safety Analyses	Counts and percentages of participants with AEs will be provided. The estimate of the DLT rate among participants treated with MK-7684A in the DLT assessment period and the 95% confidence interval for the estimate will be provided.
Interim Analyses	In Part 1, safety data will be examined on a continuous basis during the DLT evaluation window. The first interim safety review will be performed when there are 12 DLT evaluable subjects who have completed at least 2 cycles of treatment. For efficacy data, each cohort will be reviewed individually to assess efficacy signal. Details are provided in Section 9.7.
Multiplicity	No multiplicity adjustment is planned.
Sample Size and Power	Overall, approximately 330 participants may be enrolled into both parts of the study; the planned sample in Part 1 may include approximately 180 participants with relapsed/refractory disease in Cohorts A to F to be administered MK-7684A; the planned sample size in Part 2 may include approximately 120 participants with relapsed/refractory disease in Cohorts B to E to be administered MK-7684A and approximately 30 participants in Cohort G to be administered vibostolimab monotherapy. A target sample size of approximately 390 participants will be used for study planning purposes.

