Disease Type	No. of Participants	ORR	CR	Median PFS (months)	Median OS (months)	Study Treatment	References
r/r cHL	151	66%	25%	13.2	-	Pembrolizumab monotherapy	Pembrolizumab USPI, KEYNOTE-204 [U.S. Prescribing Information 2020]
r/r PMBCL	53	45%	11%	-	-	Pembrolizumab monotherapy	Pembrolizumab USPI, KEYNOTE-170 [U.S. Prescribing Information 2020]
r/r DLBCL	87	10%	-	1.9	12.2	Nivolumab monotherapy	[Ansell, S. M., et al 2019] (Failed ASCT in Checkmate 139)
r/r FL	18	11%	-	-	-	Pembrolizumab monotherapy	[Ding, W., et al 2017]
r/r MM	30	0a	0	2.7	20.2	Pembrolizumab monotherapy	[Ribrag, V., et al 2019]

Abbreviations: ASCT=autologous stem cell transplant; cHL=classic Hodgkin's Lymphoma; CR=complete response; DLBCL=Diffuse Large B-cell Lymphoma; FL= Follicular Lymphoma; MM=Multiple Myeloma; No.=number; ORR=objective response rate; OS=overall survival; PFS=Progression-free survival; PMBCL=Primary Mediastinal Large B-cell Lymphoma; r/r=relapsed/refractory; USPI=United States Prescribing Information.

-: not reported

a: Two unconfirmed responses based on laboratory assessment. Response not confirmed because participants started subsequent anticancer therapy.

A more comprehensive review of nonclinical and clinical data is included in the MK-7684 IB.

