8.11.3 Discontinued Participants Continuing to be Monitored in the Study

Participants who discontinue study treatment due to disease recurrence or start of a new anticancer therapy will have Safety Follow-up and then proceed directly to Survival Follow up Phase as outlined in the SoA (Section 1.3.4) and in Section 8.11.4.

The Discontinuation Visit should occur at the time study intervention is discontinued for any reason. If the Discontinuation Visit occurs 30 days from the last dose of study intervention, at the time of the mandatory Safety Follow-up Visit, the Discontinuation Visit procedures and any additional Safety Follow-up procedures should be performed.

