9.4.1 Efficacy/Pharmacokinetics Endpoints

After the approval of Amendment 5, the tertiary/exploratory endpoints will not be pursued after the study ends.

Secondary (Part 1)

- Objective Response Rate**

The ORR is defined as the percentage of participants who achieve a CR or PR (for MM this includes stringent CR, CR, and VGPR), as assessed by investigator per disease-specific criteria (see Appendix 8).

- Duration of Response**

For participants who show an objective response, as assessed by investigator per disease-specific criteria, duration of response is defined as the time from the first documented evidence of an objective response (CR or PR [for MM this includes stringent CR, CR, and VGPR]) until disease progression or death due to any cause, whichever occurs first.

[figure not shown]
- Disease Control Rate**

The DCR is defined as the percentage of participants who have achieved stringent CR, CR, PR (for MM, also including VGPR, MR), or have showed SD for at least 12 weeks before any evidence of progression, per disease-specific criteria (see Appendix 8) as assessed by investigator.

- Pharmacokinetic endpoints**

PK endpoints will include vibostolimab C_{trough} and C_{max} parameters.

CCI

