10.8.2 IMWG Consensus Criteria for Response and MRD in MM (Cohort E)

IMWG response criteria 2016 [Kumar, S., et al 2016].

Response assessments for Cohort E will be performed according to the IMWG criteria. The response assessment will include imaging assessments (including plasmacytoma and skeletal assessments), bone marrow results, MRD assessment, serum and urine protein results, serum FLC, and laboratory results.

Overall Response Category Definitions

IMWG MRD criteria (requires a CR as defined below):

- Sustained MRD-negative: MRD negativity in the marrow (NGF or NGS, or both) and by imaging as defined below, confirmed minimum of 1 year apart. Subsequent evaluations can be used to further specify the duration of negativity (eg, MRD-negative at 5 years).
- Flow MRD-negative: Absence of phenotypically aberrant clonal plasma cells by NGF on bone marrow aspirates using the EuroFlow standard operation procedure for MRD detection in multiple myeloma (or validated equivalent method) with a minimum sensitivity of 1 in 10^5 nucleated cells or higher.

- Sequencing MRD-negative: Absence of clonal plasma cells by NGS on bone marrow aspirate in which presence of a clone is defined as less than 2 identical sequencing reads obtained after DNA sequencing of bone marrow aspirates using the LymphoSIGHT platform (or validated equivalent method) with a minimum sensitivity of 1 in 10^5 nucleated cells or higher.
- Imaging plus MRD-negative: MRD negativity as defined by NGF or NGS plus disappearance of every area of increased tracer uptake found at baseline or a preceding PET/CT or decrease to less mediastinal blood pool SUV or decrease to less than that of surrounding normal tissue.

Standard IMWG response criteria

- Stringent CR: CR as defined below plus normal FLC ratio and absence of clonal cells in bone marrow biopsy by immunohistochemistry (κ/λ ratio $\leq 4:1$ or $\geq 1:2$ for κ and λ patients, respectively, after counting ≥ 100 plasma cells).
- Complete response: Negative immunofixation on the serum and urine and disappearance of any soft tissue plasmacytomas and $< 5\%$ plasma cells in bone marrow aspirates.
- Very good PR: Serum and urine M-protein detectable by immunofixation but not on electrophoresis or $\geq 90\%$ reduction in serum M-protein plus urine M-protein level < 100 mg per 24 h.
- Partial response:
 - $\geq 50\%$ reduction of serum M-protein plus reduction in 24 h urinary M-protein by $\geq 90\%$ or to < 200 mg per 24 h.

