 - If the serum and urine M-protein are unmeasurable, a $\geq 50\%$ decrease in the difference between involved and uninvolved FLC levels is required in place of the M-protein criteria;
 - If serum and urine M-protein are unmeasurable, and serum-free light assay is also unmeasurable, $\geq 50\%$ reduction in plasma cells is required in place of M-protein, provided baseline bone marrow plasma cell percentage was $\geq 30\%$. In addition to these criteria, if present at baseline, a $\geq 50\%$ reduction in the size (SPD) of soft tissue plasmacytomas is also required.
- Minimal response: $\geq 25\%$ but $\leq 49\%$ reduction of serum M-protein and reduction in 24-h urine M-protein by 50–89%. In addition to the above listed criteria, if present at baseline, a $\geq 50\%$ reduction in the size (SPD) of soft tissue plasmacytomas is also required.
- Stable disease: Not recommended for use as an indicator of response; stability of disease is best described by providing the time-to-progression estimates. Not meeting criteria for CR, VGPR, PR, minimal response, or PD.
- Progressive disease: Any one or more of the following criteria:
 - Increase of 25% from lowest confirmed response value in one or more of the following criteria:
 - Serum M-protein (absolute increase must be ≥ 0.5 g/dL);

- Serum M-protein increase ≥ 1 g/dL, if the lowest M component was ≥ 5 g/dL; Urine M-protein (absolute increase must be ≥ 200 mg/24 h);
- In participants without measurable serum and urine M-protein levels, the difference between involved and uninvolved FLC levels (absolute increase must be >10 mg/dL);
- In participants without measurable serum and urine M-protein levels and without measurable involved FLC levels, bone marrow plasma cell percentage irrespective of baseline status (absolute increase must be $\geq 10\%$);
- Appearance of a new lesion(s), $\geq 50\%$ increase from nadir in SPD of >1 lesion, or $\geq 50\%$ increase in the longest diameter of a previous lesion >1 cm in short axis;
- $\geq 50\%$ increase in circulating plasma cells (minimum of 200 cells per μL) if this is the only measure of disease.

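### The Section 9.1 confirmation note gives lesion-only myeloma progression no legible route to being a DOR event, and it leaves out minor response, which counts in DCR

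*Combined protocol and SAP*

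**What the plan says.** The rule stands in the note on secondary endpoints in the Section 9.1 summary table: "Stringent CR, CR, VGPR, PR, and PD in MM participants require confirmation via 2 consecutive laboratory assessments". The same note exempts lymphoma from confirmation. It makes no exception for imaging-based myeloma progression, and MR is not on the list. Sections 6.1.1 and 6.1.2 also ask for a confirmed CR in myeloma, for stopping treatment and for the second course, but give no method. The Section 9.1 note is therefore the only legible text that gives a method, and the only one that covers PD.

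Section 10.8.2 defines progression disjunctively: "Progressive disease: Any one or more of the following criteria". One of the criteria opens with "Appearance of a new lesion(s" and continues with growth of existing lesions. Imaging belongs to the assessment by design: "The response assessment will include imaging assessments (including plasmacytoma and skeletal assessments".

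DOR, in Sections 3 and 9.4.1, ends at progression or death, with no mention of confirmation. For DCR, Section 9.4.1 adds the myeloma categories ("for MM, also including VGPR, MR") and attaches the 12 weeks to SD. Section 3 and the synopsis put the 12 weeks after the whole list, MR included.

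**The concern.** Two legible statements cannot both be applied to the same participant. Someone with a new plasmacytoma or bone lesion and flat M-protein has PD under Appendix 8 but cannot meet the Section 9.1 requirement. A programmer who follows the note would not score that date as progression, so the DOR interval would run on to a later event or to censoring. Cohort E may have few responders (Table 7 shows 0 of 30 confirmed responses on PD-1 monotherapy), so one such case could shape the summary.

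The MR gap runs the other way round: the stronger category, PR, needs two assessments, while the weaker one can count on a single assessment. Cohort-level efficacy data also feed a futility review and the decision on Part 2 (Sections 4.1.1 and 4.1.2), and assessment is open-label and by the investigator. The derivation should therefore be unambiguous.

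**Working it through.** **The plan's own figure.** Section 9.9 gives 18.7% as the maximum half-width of the exact 95% CI at n = 30. The Clopper-Pearson interval is widest at 15/30: 31.3% to 68.7%, so (68.7 − 31.3)/2 = 18.7 points. It reproduces. No stated figure is in dispute; the point rests on wording.

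**Progression route by route** (Section 10.8.2 against the Section 9.1 note):

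- Serum or urine M-protein, free light chains, circulating plasma cells: laboratory values, so a second consecutive assessment is possible.
- Marrow plasma cell percentage: arguably a laboratory test. No firm conflict.
- New lesion or lesion growth: imaging. No laboratory assessment can confirm it, and neither section provides an alternative. This is the conflict.

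**Effect on DOR.** The length of the overrun, and the share of myeloma progressions that are lesion-only, are not in the documents. As pure assumption, let m responders all progress, with a share s by lesions only. The chance that at least one is affected is 1 − (1 − s)^m:

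| m | s = 0.05 | s = 0.10 | s = 0.20 |
|---|---|---|---|
| 3 | 14.3% | 27.1% | 48.8% |
| 6 | 26.5% | 46.9% | 73.8% |

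**Effect of MR on DCR.** A participant with a transient MR who stays progression-free for 12 weeks counts through SD in any case. An unconfirmed MR changes the result only if progression or missing data comes before 12 weeks, and only on the Section 9.4.1 reading. Each such participant adds 1/30 = 3.3 points.

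For illustration, take the DCR of 56.7% among 30 participants that Section 2.1.2 cites for pembrolizumab monotherapy in myeloma, which is 17/30:

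| Participants with disease control | DCR | Exact 95% CI |
|---|---|---|
| 17/30 | 56.7% | 37.4 to 74.5 |
| 18/30 (one added) | 60.0% | 40.6 to 77.3 |
| 20/30 (three added) | 66.7% | 47.2 to 82.7 |

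The documents give no rate of unconfirmed MR, so the number to add is unknown. ORR does not count MR and is untouched by this part.

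**The case against.** The best defence is that the note is a summary. Section 9.1 itself says "The comprehensive plan is provided in Section 9.2 through Section 9.12", and the DOR definitions carry no confirmation wording. Section 8.2 (criteria), Section 8.2.4 (progression) and Table 14 (censoring) are blacked out, and disease-specific censoring is partly deferred to the sSAP. An imaging exception could sit in any of them. This stands in part. A reader might infer that lesion-only progression can never be a confirmed event, but the documents support only that no legible route exists. It does not rescue the note: the sentence is unqualified and points to no exception, so it would misstate the rule even if one exists elsewhere.

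Other inferences are tempting and fail:

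- *SD is credited past a lesion progression.* Both DCR definitions stop SD at any evidence of progression, not at confirmed progression.
- *A 25% fall in serum M-protein is enough for MR.* Section 10.8.2 also requires a 50–89% reduction in urine M-protein, and plasmacytoma shrinkage if present at baseline.
- *Laboratory progression will go unconfirmed because follow-up ends.* Section 8.11.3 does say "Participants who discontinue study treatment due to disease recurrence or start of a new anticancer therapy will have Safety Follow-up" and then survival follow-up. It also requires a Discontinuation Visit, the laboratory content of the visits is blacked out, and the note sets no minimum interval between assessments.
- *Confirmation always favours the drug.* The Table 7 footnote on the cited myeloma study shows the opposite for responses: "Response not confirmed because participants started subsequent anticancer therapy".

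**Conclusion.** The point holds in a limited form. The Section 9.1 rule, as written, does not fit the lesion-based progression criterion in Appendix 8. Applied literally, it would keep lesion-only progression out of the Cohort E DOR events and lengthen DOR. A later death would still count, and if there are no responders there is no DOR to distort. The size in months cannot be derived.

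The MR part is a gap plus two DCR definitions that can be read differently. It is worth 3.3 points per affected participant at n = 30, only on the Section 9.4.1 reading and only when progression or missing data comes before 12 weeks. Under the 12-week reading of Section 3 and the synopsis the effect disappears.

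Both parts concern descriptive secondary endpoints in one cohort. The primary endpoint is safety and nothing is tested. The conclusion assumes that the blacked-out sections and the sSAP do not already settle these points; if they do, the note still needs correcting to match.

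**What to change.** For endpoint derivation only, reword the Section 9.1 note and add the same sentence to Section 10.8.2: *In MM, sCR, CR, VGPR, PR, MR and PD based on laboratory values require 2 consecutive assessments; PD based on imaging or plasmacytoma is an event at its first documentation.*

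Use one DCR definition in the synopsis, Section 3 and Section 9.4.1 that says whether the 12 weeks apply to MR. Check the new wording against Section 8.2 and Table 14. How to score a first laboratory progression followed by new therapy is a censoring choice that belongs with Table 14 and is not proposed here.

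The cost is document wording and derivation code. PR already needs a second assessment, so confirming MR should draw on the same serial laboratory data, but this cannot be checked because the schedule of activities is blacked out. The downside is that Cohort E DOR and DCR may come out slightly less favourable.

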9.2 Responsibility for Analyses/In-house Blinding

The statistical analyses of the data obtained from this study will be the responsibility of the Clinical Biostatistics department of the Sponsor.

This study is being conducted as a nonrandomized, open-label study, ie, participants, investigators, and Sponsor personnel will be aware of participant treatment assignments after each participant is enrolled and treatment is assigned.

9.3 Hypotheses/Estimation

There are no hypotheses to be tested in this study. Objectives of the study are outlined in Section 3.

9.4 Analysis Endpoints

Efficacy and safety endpoints that will be evaluated are listed below, followed by the descriptions of the derivations of selected endpoints.

9.4.1 Efficacy/Pharmacokinetics Endpoints

After the approval of Amendment 5, the tertiary/exploratory endpoints will not be pursued after the study ends.

Secondary (Part 1)

- Objective Response Rate**

The ORR is defined as the percentage of participants who achieve a CR or PR (for MM this includes stringent CR, CR, and VGPR), as assessed by investigator per disease-specific criteria (see Appendix 8).

- Duration of Response**

For participants who show an objective response, as assessed by investigator per disease-specific criteria, duration of response is defined as the time from the first documented evidence of an objective response (CR or PR [for MM this includes stringent CR, CR, and VGPR]) until disease progression or death due to any cause, whichever occurs first.

[figure not shown]
- Disease Control Rate**

The DCR is defined as the percentage of participants who have achieved stringent CR, CR, PR (for MM, also including VGPR, MR), or have showed SD for at least 12 weeks before any evidence of progression, per disease-specific criteria (see Appendix 8) as assessed by investigator.

- Pharmacokinetic endpoints**

PK endpoints will include vibostolimab C_{trough} and C_{max} parameters.

CCI

9.4.2 Safety Endpoints

The primary endpoint of Part 1 is the number and proportion of participants with DLTs, with AEs, and who discontinue study treatment due to AEs. In addition, safety and tolerability will be assessed by clinical review of all relevant parameters including AEs, laboratory tests, and vital signs.

A description of safety measures is provided in Section 8.3.

9.4.3 CCI

CCI

9.5 Analysis Populations

9.5.1 Efficacy Analysis Population

Efficacy analyses will be conducted in the APaT population, which consists of all allocated participants who received at least 1 dose of study treatment.

9.5.2 Safety Analysis Population

Safety analyses will be conducted in the APaT population, which consists of all allocated participants who received at least 1 dose of study treatment.

In Part 1, the DLT evaluable population includes the first 12 participants who meet the criteria for DLT evaluability of at least 2 cycles of treatment without discontinuation from study treatment, further detailed in Section 5.5.1. Section 4.3.4 describes the definition of DLTs.

[figure not shown]
At least 1 laboratory, vital sign, or ECG measurement obtained after at least 1 dose of study treatment is required for inclusion in the analysis of the respective safety parameter. To assess change from baseline, a baseline measurement is also required.

9.5.3 PK Populations

PK analyses will be conducted in the APaT, which consists of all allocated participants who received at least 1 dose of study treatment, who have a valid C_{trough} and/or C_{max} measurement, within the permissible visit window.

9.5.4 PRO Analysis Population

CCI

9.6 Statistical Methods

9.6.1 Statistical Methods for Efficacy Analyses

This section describes the statistical methods that address the secondary objectives. The efficacy analyses for ORR, DCR, and DOR will include responses and documented progression events that occur before second course treatment. Methods related to exploratory objectives will be described in the supplemental SAP.

Efficacy analyses will be performed for Part 1 and for combined data of Part 1 and Part 2.

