4 STUDY DESIGN

4.1 Overall Design

This is a Phase 2, open-label, nonrandomized study to evaluate the safety and efficacy of MK-7684A (a coformulation of vibostolimab and pembrolizumab) and vibostolimab monotherapy in participants with various hematological malignancies.

The study will be divided into 2 parts: signal finding (Part 1) and cohort expansion (Part 2). Overall, 330 participants may be enrolled into both parts of the study; Part 1 will include approximately 180 participants with relapsed/refractory disease in Cohorts A to F to be administered MK-7684A Q3W for up to 35 cycles; Part 2 may include approximately 120 participants with relapsed/refractory disease in Cohorts B to E to be administered MK-7684A Q3W and approximately 30 participants in Cohort G to be administered vibostolimab monotherapy Q3W for up to 35 cycles. The decision to open expansion cohorts in Part 2 will depend on the benefit and risk profile observed in Part 1 and Sponsor's development strategy.

AEs will be monitored throughout the study and graded in severity according to the guidelines outlined in the NCI CTCAE Version 5.0. Each participant will be monitored for AEs and SAEs for 30 days and 90 days, respectively, after discontinuation of study intervention.

After documenting the informed consent, suitable candidates will be screened to assess whether they meet all study eligibility criteria. Eligible participants will be assigned to 1 of 6 cohorts in Part 1 (Cohorts A to F) according to their hematologic malignancy and prior therapy received. All participants will be dosed with MK-7684A. No dose titration is currently being planned in Part 1. For Part 2, eligible participants will be alternately assigned to Cohorts B to E, according to their hematologic malignancy, to receive MK-7684A or Cohort G, to receive vibostolimab monotherapy. The study will be conducted in conformance with GCP.

After approval of Amendment 5, participants will not be offered second course treatment. The study will end 90 days after the last participant completes 35 cycles of treatment or terminates early, whichever comes first and second course option for treatment is no longer available. Participants in the Imaging Follow-up or Survival Follow-up phase will be discontinued from the study and no further imaging or participant contacts will be required.

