4.1.1 Signal Finding (Part 1)

Approximately 180 participants may be enrolled in 1 of the 6 disease-specific cohorts (approximately 30 participants per cohort) in Part 1 of the study. The cohorts will include:

- Cohort A: Participants with cHL or PMBCL who are relapsed or refractory to at least 1 line of prior therapy (cHL) or at least 2 lines of prior therapies (PMBCL). Prior therapy must not include an anti-PD-1/L1 treatment.
- Cohort B: Participants with cHL or PMBCL who are relapsed or refractory to at least 2 lines of prior therapies (cHL) or at least 3 lines of prior therapies (PMBCL). These prior therapies must include a prior anti-PD-1/L1 treatment.
- Cohort C: Participants with FL who are relapsed or refractory to at least 2 lines of prior therapy.
- Cohort D: Participants with DLBCL who are relapsed or refractory to at least 2 lines of prior therapy.
- Cohort E: Participants with MM who are relapsed or refractory to at least 3 lines of prior therapy and have exhausted all approved lines of therapy.
- Cohort F: Participants with NHL who are relapsed or refractory to at least 2 lines of prior therapy.

Further details regarding prior treatment, including SCT requirements, are described in Section 5.1 per cohort.

The primary endpoints of Part 1 of the study are DLTs, AEs, and AEs resulting in treatment discontinuation with the aim to move to cohort expansion to determine effectiveness. The definition of DLTs is provided in Section 4.3.4.

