4.1.2 Cohort Expansion (Part 2)

The decision to open expansion cohorts in Part 2 will depend on an interim review of Part 1 data per cohort of approximately 30 participants to evaluate the benefit/risk of MK-7684A in each disease type. If a favorable profile is observed in any particular disease type, Part 2 cohorts may be initiated.

Approximately 150 participants may be enrolled in 1 of the 5 cohorts (approximately 30 participants per cohort) in Part 2 of the study. Participants enrolled in Cohorts B to E (PD-1/L1 refractory, relapsed or refractory cHL or PMBCL; relapsed or refractory FL; relapsed or refractory DLBCL; and relapsed or refractory MM) will be treated with MK-7684A and those enrolled in Cohort G (PD-1/L1 refractory, relapsed or refractory cHL or PMBCL; relapsed or refractory FL; relapsed or refractory DLBCL; and relapsed or refractory MM) will be treated with vibostolimab monotherapy. Cohort allocation for Part 2 will be alternating with 1 participant for each disease type being enrolled into Cohort G first and the second into Cohort B to E, whichever is applicable. The cohorts will include:

- Cohort B: Participants with cHL or PMBCL who are relapsed or refractory to at least 2 lines of prior therapies (cHL) or at least 3 lines of prior therapies (PMBCL). These prior therapies must include an anti-PD-1/L1 treatment.
- Cohort C: Participants with FL who are relapsed or refractory to at least 2 lines of prior therapy.
- Cohort D: Participants with DLBCL who are relapsed or refractory to at least 2 lines of prior therapy.
- Cohort E: Participants with MM who are relapsed or refractory to at least 3 lines of prior therapy and have exhausted all approved lines of therapy.

- Cohort G: The following hematological malignancies, with an initial limit of 7 participants per disease type, will be included. Enrollment may be adjusted depending on opening of disease-specific cohort(s) in Part 2:
 - Participants with cHL or PMBCL who are relapsed or refractory to at least 2 lines of prior therapy (cHL) or at least 3 lines of prior therapies (PMBCL). These prior therapies must include an anti-PD-1/L1 treatment,
 - Participants with FL who are relapsed or refractory to at least 2 lines of prior therapy,
 - Participants with DLBCL who are relapsed or refractory to at least 2 lines of prior therapy, AND
 - Participants with MM who are relapsed or refractory to at least 3 lines of prior therapy and have exhausted all approved lines of therapy.

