9.9 Sample Size and Power Calculations

Part 1 (signal finding) Sample Size:

Approximately 30 participants may enroll per cohort (Cohorts A to F). With 30 participants in each cohort, the maximum half-width of the two-sided 95% exact confidence interval for ORR within each cohort is 18.7%.

Part 2 (cohort expansion) Sample Size:

Approximately 30 participants may enroll per cohort (Cohorts B to E and G) and this is the target sample size used for study planning purposes.

Since this study does not have formal hypotheses to be tested, no power calculations will be incorporated.

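### If an expansion cohort (B to E) opens partly on Part 1 responses, both listed efficacy estimates are biased upward given opening; add a Part 2-alone row beside them

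*Combined protocol and SAP*

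**What the plan says.** Section 9.6.1 lists two efficacy analysis sets: "Efficacy analyses will be performed for Part 1 and for combined data of Part 1 and Part 2". Part 2 alone is not among them. Sections 9.6.1.1 and 9.6.1.3 give ORR and DCR per cohort as plain proportions with Clopper-Pearson 95% intervals. Section 9.6.1.2 gives DOR by Kaplan-Meier. The visible text has no adjustment for how a cohort came to be expanded.

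Section 4.1.2 bases the decision to open Part 2 on an "interim review of Part 1 data per cohort of approximately 30 participants to evaluate the benefit/risk of MK-7684A in each disease type", and continues: "If a favorable profile is observed in any particular disease type, Part 2 cohorts may be initiated". Section 4.1 adds a further factor: opening will "depend on the benefit and risk profile observed in Part 1 and Sponsor's development strategy". Section 4.1.1 describes Part 1 as undertaken "with the aim to move to cohort expansion to determine effectiveness".

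Section 9.9 plans about 30 participants per cohort in each part. Part 1 has Cohorts A to F. Part 2 has Cohorts B to E and a new Cohort G on vibostolimab alone. Only B to E therefore have data in both parts.

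**The concern.** The Part 1 participants whose results are reviewed to open a cohort are the same people who make up half of that cohort's pooled estimate. If response is part of what counts as favorable, cohorts with a lucky Part 1 are more likely to be expanded. Their Part 1 rate then tends to exceed the truth, and pooling dilutes this excess without removing it. The Clopper-Pearson interval on the pooled count assumes an unselected binomial sample, so its lower limit can lie above the true rate more often than the nominal 2.5%.

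What is at stake is how an expanded cohort's ORR is read. Table 7 puts PD-1 monotherapy at 10% for DLBCL and 11% for FL. Against rates that low, a few points of upward bias is a large relative error. The participants who could show whether the Part 1 signal held up are enrolled in Part 2, but the plan does not list their results separately.

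**Working it through.** **The plan's own figure.** Section 9.9 states: "With 30 participants in each cohort, the maximum half-width of the two-sided 95% exact confidence interval for ORR within each cohort is 18.7" (percent). With n = 30 the widest Clopper-Pearson interval is at x = 15, running from 31.30% to 68.70%. The half-width is (68.70 − 31.30)/2 = 18.7 points, so the figure reproduces. With n = 60 the widest interval is at x = 30, from 36.81% to 63.19%, a half-width of 13.2 points.

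**Inputs.** n1 = n2 = 30 (Section 9.9). A true ORR of 10% is taken as an illustration from the DLBCL row of Table 7; 20% and 30% are assumptions. The opening rule is also an assumption: open if Part 1 has X1 ≥ r responders of 30. The documents show no numeric rule.

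**Formulas.** X1 and X2 are independent Binomial(30, p).
- Part 1 mean given opening: E[X1 | X1 ≥ r]/30.
- Pooled mean given opening: (E[X1 | X1 ≥ r]/30 + p)/2. Because n1 = n2, the pooled bias is exactly half the Part 1 bias.
- Part 2 mean given opening: p, because X2 is independent of the decision. Bias 0.
- Pooled coverage given opening: the probability, over X1 truncated at r plus X2, that the Clopper-Pearson interval on n = 60 contains p.

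**One case in full.** With p = 10% and r = 4, P(open) = 0.353 and E[X1 | X1 ≥ 4] = 4.81. The Part 1 mean is 4.81/30 = 16.0% (bias +6.0). The pooled mean is (16.0 + 10.0)/2 = 13.0% (bias +3.0).

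| True ORR | Open at | P(open) | Part 1 bias | Pooled bias | Pooled 95% CI coverage | Lower limit above truth |
|---|---|---|---|---|---|---|
| 10% | ≥3/30 | 0.59 | +3.6 | +1.8 | 97.5% | 2.5% |
| 10% | ≥4/30 | 0.35 | +6.0 | +3.0 | 96.0% | 4.0% |
| 10% | ≥5/30 | 0.17 | +8.7 | +4.4 | 92.8% | 7.2% |
| 10% | ≥6/30 | 0.07 | +11.7 | +5.8 | 86.4% | 13.6% |
| 20% | ≥6/30 | 0.57 | +5.0 | +2.5 | 96.2% | 3.8% |
| 20% | ≥9/30 | 0.13 | +12.6 | +6.3 | 86.8% | 13.2% |
| 30% | ≥5/30 | 0.97 | +0.6 | +0.3 | 97.2% | 2.0% |
| 30% | ≥9/30 | 0.57 | +5.8 | +2.9 | 96.6% | 3.4% |

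Biases are in percentage points. Part 2 alone has zero bias in every row.

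**Bias against variance.** Root-mean-square error given opening, pooled against Part 2 alone, in points:
- True ORR 10%: 4.4 v 5.5 (≥4), 5.4 v 5.5 (≥5), 6.6 v 5.5 (≥6).
- True ORR 20%: 5.6 v 7.3 (≥7), 6.4 v 7.3 (≥8), 7.5 v 7.3 (≥9).

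The pooled estimate is closer to the truth on average in four of these six cases. It loses only under the strictest rule at each rate, where opening is rare.

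**The case against.** Several stronger readings are tempting, and the documents do not support them.

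- *The expansion participants' ORR is biased.* It is not. They are new participants, and their own rate is independent of the opening decision. The biased quantities are the Part 1 and pooled rates of a cohort that opened.
- *No unbiased estimate is planned.* This is true only given opening. Part 1 ORR is reported for every cohort, opened or not, so taken over all outcomes the expansion decision does not bias it (any effect of the 12-participant futility look is a separate matter). If one reports Part 1 for unopened cohorts and the pooled rate for opened ones, the average bias is not upward: at a true ORR of 10% and opening at ≥4/30 it is −1.1 points.
- *Part 2 alone should be the headline estimate.* The root-mean-square errors above show that this is a trade of bias against variance, not a correction of an error.
- *Error rates are inflated.* Section 9.3 tests no hypotheses, so there is no type I error to inflate. The harm is to estimation and coverage.

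Other points limit the concern. Opening rests on benefit/risk and sponsor strategy, not on a visible response cutoff. Sections 9.7 and 9.8 are redacted and the supplemental SAP is not available, so nothing can be inferred from either. ORR, DCR and DOR are secondary objectives stated for Part 1, Part 2 is optional, and the current intervention table (Table 9) covers Part 1 only. All of this stands, and it keeps the point small.

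The best remaining argument is that a reader can subtract Part 1 responders from the pooled count. That works for ORR and DCR at a common data cutoff. It fails for DOR and for differing cutoffs, and it gives no warning about the pooled interval.

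**Conclusion.** The point holds in a limited form, as a cheap improvement. If any of Cohorts B to E opens partly because of Part 1 responses, both listed estimates for that cohort are biased upward given opening, and the pooled interval can under-cover. The estimate free of this selection is not listed. The pooled bias is about 0 to 6 percentage points with 30 + 30 participants. It is near zero under a lenient rule and largest where opening is improbable. That range rests on assumed response cutoffs and assumed true rates; the more the decision turns on safety or strategy instead of response, the smaller the bias. Cohorts A and F are not expanded and Cohort G has no Part 1 data to pool, so none of the three is affected.

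**What to change.** In Section 9.6.1, extend the list of efficacy analyses with Part 2 alone for each expanded cohort (B to E): ORR and DCR with exact 95% intervals, and DOR, reported beside the pooled result. Label the Part 1 and pooled results of expanded cohorts as conditional on selection from Part 1. Keep the pooled analysis. A bias-adjusted pooled estimator is not asked for, since it would need a prespecified numeric opening rule.

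The cost is a line of SAP text and one extra table, with no new data or participants. The Part 2-only interval is wider, with a maximum half-width of 18.7 points at n = 30 against 13.2 at n = 60, so it should be read with the pooled result.
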